3.0 SUBJECT SELECTION & RECRUITMENT

3.1 INCLUSION CRITERIA

One hundred and fourty participants (at least 50% female) between the ages of 18-30 years will be recruited from the surrounding area.

The age range was selected based on a recent meta-analysis by my colleagues and I, which demonstrated that participants ages 18-30 have different cardiovascular reactivity compared to those over 30⁴³. The sample will be representative of the greater Waco demographics.

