3.3 RECRUITMENT

We plan to recruit participants to test over a four-year period. This should provide ample time to recruit participants. It also allows us time to alter our recruitment efforts if we are not meeting targets. We will evaluate recruitment every two months to make sure we are on track to hit our targeted number of participants. Based on previous work by our laboratory and others in the area, we will use recruitment strategies that are effective within our community. Specifically, we will advertise for participants at Baylor University using the participant subject pool, on flyers across campus, through ads at local shops and stores, and on local social media sites.

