4.0 RESEARCH DESIGN, METHODS, AND STUDY ACTIVITIES

Rationale: Previous research has identified areas of the brain associated with psychological stress and cardiovascular responses to stress; however, this research has not examined what is thought to be the most detrimental responses to stress, known as metabolically exaggerated²⁸. Participants will have their metabolic and cardiovascular responses to stress measured, as well as undergo an fMRI scan to examine their stressor-evoked neural responses. The hypothesis here is that a multivariate pattern of stressor-evoked responses will be able to predict the magnitude to which cardiovascular responses to stress are excessive of metabolic demand and that this pattern will encompass areas implicated in stress processing and cardiovascular control. This aim will be vital in elucidating the neurophysiological pathways of metabolically excessive cardiovascular responses to stress by identifying key brain areas that are related to the peripheral responses.

Design: The protocol will be the same for all participants.

Duration: Visit 1 will take approximately 2 hours and Visit 2 will take approximately 2 hours. The total commitment will be 4 hours.

Visit 1 Protocol: Visit 1 is designed to determine the additional heart rate (i.e., degree to which each participant's response to stress is metabolically inappropriate). Participants will come to the laboratory to engage in a standard stress testing paradigm. Following instrumentation with cardiovascular equipment and body metabolic measuring equipment, participants will be given 20 minutes to adapt to the laboratory environment. This will be followed by a 10-minute formal resting baseline, and 18-minutes of acute psychological stress tasks (MSIT and Stroop task), see description below⁹. This will then be followed by four 4-minute bouts of cycling exercise incrementally increasing in demand¹⁴ and will include with a maximal exercise test (described below). Participants will fill out questionnaires regarding demographics and health behaviors.

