Visit 1 Measurements: Cardiovascular activity will be measured continuously⁴³ throughout the protocol using electrocardiogram and will be calculated for each minute of the protocol using Mindware Kubios processing software³⁴. Body metabolic rate, indexed by oxygen consumption, will be measured on a breath-by-breath basis assessing ventilation and analyzing inspired and expired gas composition using an integrated system. Metabolic rate will then be averaged for each minute. Additional heart rate will be calculated by first computing individual regressions of oxygen consumption on heart rate using data from rest and each of the 4-minute bouts of the graded exercise test¹⁴. The computed regressions for each participant will then be used, with each individual's observed oxygen consumption recorded during stress, to "predict" what heart rate should be during baseline and during the MSIT (acute psychological stress). The difference between observed heart rate and predicted heart rate will be additional heart rate, which represents heart rate in excess of body metabolic demand.

Visit 2 Protocol: Visit 2 is designed to measure stressor-evoked neural activity, required to develop multivariate analyses to predict metabolically excessive responses (i.e., additional heart rate). The same 150 participants will come to the VINS 17 CoE to engage in a functional magnetic resonance imaging protocol. The protocol will consist of a structural scan, followed by a functional scan during which participants will engage in the MSIT and Stroop.

Visit 2 Measurements: Functional and structural images will be obtained on a Philips Ingenia 3.0 Tesla Omega MRI scanner equipped with a 32-channel head coil. Blood-oxygen level-dependent (BOLD) images will be acquired over the stressor

[figure not shown]
period with the following parameters: FOV = 205 x 205 mm², matrix size = 64 x 64 mm², TR = 2,000 ms, TE = 28 ms, and FA = 90°. Functional scans will be obtained at rest and during an acute psychological stress task (MSIT).

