6.0 STATISTICAL ANALYSIS

All participants will receive a unique ID for the study. IDs will be given starting with the number 9000. Questionnaire data will be collected through the Qualtrics survey system using tablets in the laboratory. Qualtrics will store the data on an encrypted server that will only be accessed by the Co-Investigator, primary RA, and students working on the study.

Analytic plan: Averages of the main study variables will be calculated for the main analyses of examining cardiovascular, metabolic, and neural activity at rest and during the acute psychological stress task. Reactivity will be calculated as: Stress activity – Baseline activity. fMRI data will be preprocessed and analyzed with statistical parametric mapping software (SPM12; <http://www.fil.ion.ucl.ac.uk/spm>) using established realignment, co-registration, smoothing, and motion correction analyses³⁸. Stressor-evoked brain activation will be determined by comparing the BOLD signal activity during the incongruent (stress) versus congruent (control) condition^{9,38}. For the analyses between stressor-evoked cardiovascular activity and stressor-evoked neural activity, machine learning techniques will be used to generate a multivariate pattern (3D regression weight map) that relates to heart rate and metabolic responses to stress. The study will then test if this generated multivariate pattern can reliably predict cardiovascular and metabolic responses to stress. Recent papers examining brain multivariate pattern prediction of cardiovascular responses to stress found the between subjects correlations to be relatively small, $r = \sim .20$. Based on these results, with alpha set at .05 and power = .80, it is estimated we will need a sample of at least $N = 140$.

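### The stated sample size of 140 does not follow from r of about .20, alpha .05 and power .80; at r = .20 it gives about 66% power two-sided or 77% one-sided

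*Combined protocol and SAP*

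**What the plan says.** The only power statement is in the analytic plan of Section 6.0. It reports that earlier work on brain-pattern prediction of cardiovascular stress responses "found the between subjects correlations to be relatively small, $r = \sim .20", and from this concludes: "with alpha set at .05 and power = .80, it is estimated we will need a sample of at least $N = 140". It names no test, sidedness or software.

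The analysis to be powered is described just before: "The study will then test if this generated multivariate pattern can reliably predict cardiovascular and metabolic responses to stress". The hypothesis in Section 4.0 is worded in one direction: "a multivariate pattern of stressor-evoked responses will be able to predict the magnitude".

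Two participant numbers appear. Section 3.1 reads: "One hundred and fourty participants (at least 50% female) between the ages of 18-30 years will be recruited". The Visit 2 protocol in Section 4.0 reads: "The same 150 participants will come to the VINS 17 CoE". Neither these sections nor Section 6.0 gives an allowance for withdrawn participants or unusable scans.

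**The concern.** A correlation of .20 at alpha .05 and 80% power is a standard calculation, and 140 is well below the usual two-sided answer. It is also below the one-sided answer, though by less. Because sidedness is missing, a reader cannot tell whether the shortfall in power is slight or serious.

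The figure matters because it sets the target against which Section 3.3 tracks recruitment: "We will evaluate recruitment every two months to make sure we are on track to hit our targeted number of participants". It also governs how a null result would be read. If readers believe the study had 80% power for r = .20, they will take a null finding as stronger evidence against the hypothesis than it is, mainly if the test is two-sided.

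The required number and the number recruited are both 140, so any participant without usable data from both visits takes the analysed sample below the stated minimum. The reference to 150 at Visit 2 leaves the intended size itself unclear.

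**Working it through.** **Inputs from Section 6.0:** r about .20, alpha .05, power .80, stated N = 140. **Not stated:** sidedness (both are tried) and the test. I assume one correlation tested against zero in independent participants, since the plan justifies N by between-subjects correlations.

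**1. Required N at r = .20, Fisher z.** N = ((z_alpha + z_power) / atanh(r))² + 3, with atanh(.20) = .2027 and z_power = .8416.
- Two-sided: ((1.9600 + .8416) / .2027)² + 3 = 193.97, so 194.
- One-sided: ((1.6449 + .8416) / .2027)² + 3 = 153.43, so 154.

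The noncentral t calculation (N − 2 degrees of freedom, noncentrality r√N / √(1 − r²)) gives 191 and 150. The plan's 140 is not reproduced by either method.

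**2. Power at N = 140, r = .20.** Power = Φ(atanh(r)·√(N − 3) − z_alpha), where .2027 × √137 = 2.373.
- Two-sided: Φ(2.373 − 1.960) = .660.
- One-sided: Φ(2.373 − 1.645) = .767.

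Noncentral t gives .669 and .776. Simulation of bivariate normal data (200,000 replicates) gives .664 and .770.

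**3. Does the word 'about' rescue 140?** N for 80% power, Fisher z with noncentral t in brackets:

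| r | Two-sided | One-sided |
|---|---|---|
| .18 | 240 (237) | 190 (187) |
| .195 | 205 (201) | 162 (158) |
| .20 | 194 (191) | 154 (150) |
| .205 | 185 (181) | 146 (143) |
| .21 | 176 (173) | 140 (136) |
| .22 | 160 (157) | 127 (123) |
| .235 | 140 (137) | 111 (108) |

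If r rounds to .20 at two decimals (.195 to .205, my assumption), power at N = 140 is .64 to .69 two-sided and .75 to .79 one-sided. Over a looser .18 to .22 (also assumed), it is .57 to .75 two-sided, always below .80, and .69 to .84 one-sided, which straddles .80.

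**4. Correlation for which 140 gives 80% power.** Fisher z: r = tanh((z_alpha + z_power) / √137).
- Two-sided: tanh(2.8016 / 11.705) = .235 (.232 by noncentral t).
- One-sided: tanh(2.4865 / 11.705) = .209 (.207 by noncentral t).

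**5. If 150 is the intended number.** Power at r = .20 is .69 to .70 two-sided and .79 to .80 one-sided.

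**6. If some of the 140 are unusable** (illustrative losses, not from the plan; Fisher z, r = .20):

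| Loss | Analysed | Two-sided | One-sided |
|---|---|---|---|
| 5% | 133 | .64 | .75 |
| 10% | 126 | .61 | .73 |
| 20% | 112 | .56 | .68 |

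**The case against.** The plan does not claim that r is exactly .20; it gives an approximate value drawn from several papers. The hypothesis is directional, and a negative correlation between predicted and observed responses would not support it, so a one-sided test is a natural reading. One-sided at r = .205, the noncentral t method gives 143, close to 140; at r = .21, Fisher z gives exactly 140. On that reading the gap is about 3 percentage points and could come from rounding. If 150 is the operative number, one-sided power is essentially as planned.

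This limits the size of the one-sided problem, and I accept it to that extent. It does not make the statement correct: the plan declares neither a one-sided test nor r = .21, and no rounding to .20 explains 140 two-sided. Nor do the documents say where 150 comes from.

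It can also be said that the real analysis trains and tests a machine-learning pattern, so a simple correlation calculation may not describe its power. That is fair, and actual power could differ. But the plan bases its own number on correlations, and Section 6.0 specifies no hold-out or cross-validation split from which another calculation could be made.

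**Conclusion.** The concern holds. At r = .20, the stated N is short by 51 to 54 participants two-sided (191 to 194 less 140) or 10 to 14 one-sided (150 to 154 less 140). The chance of missing a true effect of that size is about 34% or 23% against a planned 20%, an excess of about 14 or 3 percentage points. Which applies depends on a choice the plan leaves open. Separately, 140 and 150 contradict each other, and no margin for lost data is stated.

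These figures rest on a simple correlation test, independent participants and complete data on everyone counted. The two-sided conclusion holds across every reading of r from .18 to .22; the one-sided conclusion is sensitive to the exact r.

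**What to change.** Enrolment need not rise. In this order:

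1. State in Section 6.0 whether the test is one-sided or two-sided.
2. Reconcile 140 and 150. Use one number in Sections 3.1, 4.0 and 6.0, label it as recruited or analysable, and state the allowance for unusable data, even if it is none.
3. Replace the power sentence with the achieved figure. For 140 analysable participants:
   - *If two-sided:* For a simple correlation test with 140 analysable participants, power to detect r = .20 is about 66% at two-sided alpha .05; power reaches 80% for r of .235 or more.
   - *If one-sided:* For a simple correlation test with 140 analysable participants, power to detect r = .20 is about 77% at one-sided alpha .05; power reaches 80% for r of .209 or more.

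If the settled number is 150 analysable, the power figures become 69 to 70% and 79 to 80%. For any other analysable number, recompute with the same formula. Keep the words on a simple correlation test, so that the figure is not taken as the power of the full pattern-training procedure.

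The cost is wording, a less favourable power figure, and a commitment to a sidedness.

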
Brain-imaging studies of stressor-evoked cardiovascular reactivity. Recent meta-analyses have identified core components of a broad network of forebrain systems involved stressor-evoked changes in cardiovascular activity^{25,30-33}. These forebrain areas functionally interact with one another to modulate visceromotor and viscerosensory functions of cell groups within areas that govern and monitor autonomic and neuroendocrine outflow to the heart and blood vessels in coordination with behavioral actions and motivated dispositions to act³⁴⁻³⁶. Recent studies address previous limitations in stressor-evoked neuroimaging research by examining how patterns of responses, rather than voxel-by-voxel analyses, predict the likelihood of a certain magnitude of cardiovascular response^{37,38}. Using multivariate and cross-validation methods allows for more rigorous statistical testing and more generalizable results that could identify a brain phenotype that reflects CVD risk^{38,39}. Although it is the metabolically-disproportionate, stressor-evoked, cardiovascular reactions that are thought to most closely link with pathophysiological changes in vulnerable individuals, previous work in the field has only examined the neural correlates of stressor-evoked cardiovascular changes (i.e., cardiovascular reactivity)^{9,25,37,40-42}. This study will be the first study to directly test the hypothesis that metabolically-disproportionate, stressor-evoked, cardiovascular reactions are associated with ‘visceral prediction’ errors²⁸.

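### Section 6.0 sizes the pattern-prediction test as a simple correlation and names no validation scheme, sidedness or null distribution, so the stated alpha of .05 and power of .80 are not secured by any of the evident ways of running it

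*Combined protocol and SAP*

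**What the plan says.** In the combined protocol and SAP, the analytic plan in Section 6.0 describes two steps. Machine learning produces a weight map that relates stressor-evoked brain activity to heart rate and metabolic responses. The study then tests whether that map reliably predicts those responses. The section gives no algorithm, number of features, tuning rule, cross-validation scheme, hold-out sample, test statistic or reference distribution.

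The only inferential figures are in the sample-size sentence. It says that earlier pattern-prediction papers "found the between subjects correlations to be relatively small", at about .20, and concludes that "with alpha set at .05 and power = .80, it is estimated we will need a sample of at least" 140. Sidedness is not given; the text says only "with alpha set at .05".

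Cross-validation appears once, in the brain-imaging paragraph of Section 1.0, as a merit of the approach: "Using multivariate and cross-validation methods allows for more rigorous statistical testing and more generalizable results". The rationale in Section 4.0 makes prediction of metabolically excessive responses from the brain pattern the stated hypothesis.

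**The concern.** Alpha, power and N are presented as properties of the prediction test, but they come from a calculation for one simple correlation between independent pairs. In cross-validation each participant is predicted by a model trained on the others, so the predictions share training data. Under a true null the pooled predicted-observed r is then more variable than the ordinary test assumes, and its mean often falls slightly below zero. The first effect raises the false-positive rate. The second lowers it and comes to dominate under heavy shrinkage.

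At stake is the test of the study's stated hypothesis. Depending on analysis choices not yet made, a nominal 5% test could roughly double its error rate, or become so strict that a real pattern is missed.

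**Working it through.** **Inputs.** From Section 6.0: r = .20, alpha = .05, power = .80, N = 140. Assumed because not stated: sidedness (both shown), the learner, its penalty, the number of features and the folds (ranges shown).

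**1. The plan's own figure.** By Fisher z, N = ((z_alpha + z_beta)/atanh r)² + 3, with atanh(.20) = .2027 and z_beta = .8416.

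- One-sided: ((1.6449 + .8416)/.2027)² + 3 = 153.4, so 154.
- Two-sided: ((1.9600 + .8416)/.2027)² + 3 = 194.0, so 194.

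Other standard variants, including noncentral t, give 149 to 155 one-sided and 189 to 197 two-sided. None gives 140. N = 140 results from r = .21 one-sided or r = .235 two-sided.

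**2. Power of the ordinary test at N = 140.** Power = Φ(atanh(.20)·√(N − 3) − z_alpha), with .2027 × √137 = 2.373.

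- One-sided: Φ(2.373 − 1.645) = Φ(.728) = 77%.
- Two-sided: Φ(2.373 − 1.960) = Φ(.413) = 66%.

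**3. Independent hold-out (assumed 70/70 split).** .2027 × √67 = 1.659.

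- One-sided: Φ(.015) = 51%.
- Two-sided: Φ(−.300) = 38%.

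With 100 participants in the test set, .2027 × √97 = 1.997, giving Φ(.352) = 64% and Φ(.037) = 51%. These figures assume that the smaller training set still yields r = .20. In simulation the hold-out's one-sided error was 4.9%, so the level is kept but the power is not.

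**4. Cross-validation judged by the ordinary null.** The ordinary null SD of r is 1/√139 = .085, and the one-sided 5% critical r is .140. Null outcomes, independent of 1,000 Gaussian features, were put through 5- or 10-fold cross-validation at N = 140, with 7,500 outcomes per setting. In the table, k is the feature's rank and the ridge penalty is a multiple of the mean diagonal of the training Gram matrix.

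| Learner | Feature variance | Folds | Mean r | SD of r | Rejected, one-sided 5% | Calibrated critical r |
|---|---|---|---|---|---|---|
| Ridge, 0.01 | flat | 10 | −.016 | .117 | 9.8% | .180 |
| Ridge, 0.01 | 1/k | 10 | −.008 | .117 | 10.7% | .188 |
| Ridge, 0.1 | 1/k | 5 | −.010 | .118 | 10.0% | .186 |
| Ridge, 0.1 | 1/k² | 10 | −.027 | .119 | 8.0% | .163 |
| 100 components | 1/k | 10 | −.011 | .114 | 9.9% | .178 |
| 30 components | 1/k | 10 | −.029 | .118 | 7.2% | .160 |
| Ridge, 0.01, training mean not added back | 1/k | 10 | .004 | .117 | 12.8% | .196 |

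A normal approximation confirms the mechanism. For the third row, 1 − Φ((.140 + .010)/.118) = 1 − Φ(1.27) = 10%.

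Over a wider set of penalties, feature counts and folds, including leave-one-out, the SD was about .11 to .14. Strong penalties gave about 0.2% to 3% one-sided. A two-sided nominal 5% test rejected 15% to 30% in total, but only 0.9% to 8.6% in the positive tail, against the intended 2.5%.

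**5. The calibrated alternative.** Permuting the outcome and rerunning the whole cross-validation gave 25/400 = 6.3% one-sided. With a Monte Carlo standard error of √(.05 × .95/400) = 1.1 points, that is consistent with 5%. Other settings gave 2.9% to 5.9% (375 data sets each).

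**6. Illustrative power with a calibrated critical r.** This assumes an expected cross-validated r of .20 with ordinary sampling error.

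- Critical r .16: Φ((.2027 − .1614) × 11.70) = Φ(.48) = 69%.
- Critical r .19: Φ((.2027 − .1923) × 11.70) = Φ(.12) = 55%.

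**The case against.** The strongest reply is that the plan never commits to the faulty test. The r of about .20 is a planning effect size, not a declared test statistic. Cross-validation appears only in the background. Generating a pattern and then testing it is compatible with a hold-out, which keeps 5%. All of this stands: the defect is an unspecified test, not a documented wrong one.

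A reader might infer that the test rejects a true null 9% to 11% of the time. The documents do not support a fixed figure. They give no learner, penalty, feature count or folds, and plausible choices run from under 1% to about 13%. A reader might also infer that any out-of-sample test shares the fault, which the hold-out result refutes. The two-sided total of 15% to 30% should not be taken as the rate of false claims of prediction, because in many settings more than half of those rejections are negative correlations. Nor is this the study's only analysis: Section 6.0 also plans comparisons of rest and stress activity, and Section 2.0 calls the predictive pattern a long-term goal.

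On sample size, it is fair to say that .20 is approximate and that r = .21 one-sided does give 140. But the plan states neither .21 nor one-sided testing, and that reading still describes a simple correlation.

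The reply does not rescue the stated figures. Leaving the test open leaves alpha and power without a defined meaning, and none of the routes examined delivers both at r = .20 and N = 140.

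**Conclusion.** The point holds in conditional form. Section 6.0 attaches alpha .05, power .80 and N = 140 to a prediction test that it does not define, using a simple-correlation calculation. At r = .20 that calculation gives 77% (one-sided) or 66% (two-sided) power even on its own terms. A 70/70 hold-out gives about 51% or 38%. Cross-validation judged by the ordinary null gives a one-sided error between under 1% and about 13%: about 9% to 11% with light shrinkage, and roughly 3% or less with heavy shrinkage, where power is lost.

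The hold-out and ordinary-test powers rest on r = .20 and the Fisher approximation. The cross-validation rates rest on linear learners, Gaussian features and fixed penalties rather than real fMRI maps, and should be quoted only as a range under those assumptions. The direction is firmer than any single rate: the null spread of r is wider than the ordinary test assumes, and no calibrated test is named.

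**What to change.** In Section 6.0:

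- State the learner, the tuning rule, the cross-validation scheme and a one-sided test of the predicted-observed r.
- Take p from a permutation test that shuffles the outcome across participants and reruns the whole pipeline, tuning included, with enough permutations for a stable p.
- Replace the stated power with the figure simulated for that test at N = 140. This does not require enrolling more participants.
- Reconcile 140 (Sections 3.1 and 6.0) with the Visit 2 text in Section 4.0, which says "The same 150 participants will come to the VINS 17 CoE", so that the power statement refers to one N.

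The cost is one paragraph, computing time and a less favourable stated power, illustratively about 55% to 69% if the critical r lies between .16 and .19. Visits and measurements are unchanged. The text should be settled before the prediction analysis is run, because the error rate depends on choices that would otherwise be made with the data in hand.
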